#### *Diagnostic Interventions*

A peripheral venous catheter (18 Gauge) will be inserted distally in an upper extremity for the measurement of central venous pressure. A blood sample will be drawn for baseline kidney function at initial visit.. Mean capillary filling pressure will be obtained by rapid occlusion of arm circulation with high-pressurized cuff as shown in Figure 2. Inert gas rebreathing apparatus will be applied for measurement of cardiac output during exercise testing.

#### Venous puncture

A needle will be used to draw a basic metabolic profile at Visit 1 and Visit 6 to assess renal function. The minimal amount of blood (~2 mL) will be obtained one time at each visit.

#### Venous Cannulation

A catheter will be placed into an antecubital vein and will be connected to a pressure monitor. Venous pressures will be monitored prior to beginning exercise and then every 1 minute during exercise and after exercise during the recovery period (5 minutes). Venous pressures measured using a peripheral venous line has previously been shown to be reflective of central venous pressure in Fontan patients. The same venous cannula will be used for obtaining mean capillary filling pressure. This same needle can be used for baseline basic metabolic profile blood draw at first visit.

#### Baseline Spirometry

Baseline spirometry will be performed as the best of 3 good respiratory maneuvers, directed by an experienced operator. The predicted forced expiratory volume in 1 second (FEV1) will be calculated from their height and weight and then the participant will be asked to provide three good attempts at producing their FEV1. This will be then used to calculate their maximum voluntary ventilation (MVV) with the following calculation: MVV = FEV1 x 40.

#### Maximal Exercise Testing/Ramp Protocol

The ParvoMedics Exercise cart will be used for cardiopulmonary exercise testing in all cases. The equipment will be calibrated and operated to the standards specified in the ATS/ACCP (2003) guidelines. Participants will initially sit at rest on the electromagnetically-braked cycle ergometer for three minutes while baseline cardiopulmonary variables are recorded (baseline phase). This will be followed by three minutes of unloaded cycling at a cadence of 60 rpm, after which the power output will be increased gradually to reach maximum exercise in 8-10 minutes. . Talking to the study subjects will be kept to a

minimum. Participants will be asked to maintain a cadence of 60 rpm throughout the test until volitional intolerance. The power output will be immediately reduced and the cardiopulmonary variables monitored for at least 2 minutes (recovery phase).

The Innocor system (Innovision, Odense, Denmark) will be used to assess noninvasive cardiac output (CO) measurements based on the Inert Gas Rebreathing (IGR) method. Innocor is in clinical use at this institution and forms part of routine clinical exercise testing. The IGR method is based on the perfusion-related change in alveolar concentration of a soluble inert gas inspired from a closed system. A second insoluble marker gas is used for the determination of lung volume. The Innocor device consists of a closed system, including a three-way automatic respiratory valve connecting a facemask; a rebreathing bag, which is filled before commencement of the rebreathing maneuver to a calibrated volume; and an infrared photoacoustic gas analyzer. The inspired gas of this system contains 90% room air, whereas the remaining 10% is composed of a mixture of oxygen with 5% nitrous oxide (N2O) and 1% sulfur hexafluoride (SF6), resulting in inspired concentrations of 0.5% N2O as soluble and 0.1% of SF6 as non-soluble component. The soluble component of the inspired gas is absorbed by the pulmonary blood flow with an absorption rate proportional to the pulmonary blood flow. In the absence of shunts, pulmonary blood flow is equivalent to CO. SF6, as non-soluble component of the inspired gas, remains unaffected by pulmonary blood flow and allows determination of lung volumes. For the measurement, patients must breathe the gas mixture from the closed system during a period of a half minute. The components of the test gas as well as the expired carbon dioxide (CO2) are continuously and permanently recorded at the mouthpiece and computed by a photoacoustic gas-analyzer.

The Innocor system will be used to assess pulmonary blood flow at rest and at peak exercise, i.e. 2 time points. Because steady breathing with constant amplitude is required to obtain reliable measurements, all participants will be familiarized with the exercise protocol and practiced the rebreathing maneuvers before the test, and we will only obtain data with the Innocor system just prior to beginning the exercise test and at peak exercise to limit any confounding of the regular exercise test data, as switching from one mouthpiece to another is required and this will minimize inaccurate data during this transition.

### **Liver Ultrasound**

A Toshiba Aplio i800 (or equivalent) ultrasound system will be used for this study and is FDA-approved for clinical use in humans. Research imaging will include liver assessments of stiffness (ultrasound shear wave elastography), and blood flow (gray-scale and Doppler imaging). Each of these forms of imaging is FDA approved and used as part of routine care for other patients at CCHMC. While a formal imaging report will not be rendered, images will be reviewed by a study investigator or other radiologist for clinically important incidental findings. Any such abnormality would be reported to the patient's physician. All images will be stored on the Department of Radiology research PACS, with exams and images labeled using subject study ID number and date of imaging/visit. No other HIPAA-defined protected health information will be stored in the research PACS system for this investigation. Research images will be kept for the duration of the study or as long as required by CCHMC or law. All study patients should be fasting prior the ultrasound imaging being performed.

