### Abstract/Brief Overview:

Each year over 1,200 Fontan operations are performed on children in the United States with a congenital heart defect resulting in single ventricle physiology. This translates to over 2,500 Fontan operations annually world-wide and thousands more infants born with one functional ventricle who don't reach Fontan physiology. Fontan physiology describes a circulation where the only ventricle pumps blood to the body and blood flow to the lungs is passive, down a pressure gradient, without a pumping ventricle. Unfortunately, there can be significant long-term morbidity associated with the Fontan physiology, largely related to chronic venous congestion and difficulty traversing the pulmonary vasculature without a ventricle to power it. Nitrate based medications such as isosorbide dinitrate (ISDN) have been used in adults with heart failure demonstrating improved survival, ejection fraction, and exercise tolerance in select populations. In pediatric patients, they have recently been shown to increase venous capacitance, thereby decreasing central venous pressure within the Fontan circulation. Central venous pressure is a critical indicator of Fontan function and an instigator of morbidities in these patients. We will investigate the safety and preliminary efficacy of ISDN therapy to reduce venous congestion and improve exercise tolerance in children and adults after the Fontan operation. This will be accomplished by recruiting 15 Fontan physiology patients from the Cincinnati Children's Fontan clinic and University of Kentucky Pediatric Cardiology clinic for the investigation. We will non-invasively measure both central venous pressures at rest and during graded cardiopulmonary exercise testing. In addition we will obtain a measurement of liver stiffness before and after a 4-week regimen of ISDN therapy. Patients will be seen twice in clinic, once before and after ISDN therapy, and phone calls will be made to ensure safety, compliance, and make appropriate alterations to medications throughout the study period. Pre- and post-intervention central venous pressure and exercise tolerance will be compared.

In this investigation we hypothesize the following:

- Isosorbide dinitrate will lower central venous pressure
- The better hemodynamics associated with central vasodilation will result in greater exercise endurance and improved liver stiffness

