**2. To ensure low rate of side-effects in polypharmacy of Fontan patients**

### **Study Design:**

This will be a single arm, two-center prospective clinical trial of ISDN (up to 30 mg, 3 times daily) in pediatric and adult patients greater than 9 years old who have undergone the Fontan operation and do not have Fontan failure. The dose selected was based on current treatment protocols at the Cincinnati

Fontan clinic, literature review, and discussion with adult heart failure specialists. Fifteen patients will be enrolled from our Cincinnati Children's Fontan Clinic and collaborating pediatric cardiology clinic at the University of Kentucky. We will test the hypothesis that ISDN administration over 1-month period will be safely tolerated and improve exercise venous pressure responses, as well as exercise tolerance in Fontan patients. Our primary end point will be the change in exercise tolerance after 1 month of ISDN therapy. Secondary end points will include change in central venous pressure and cardiac output at rest and during exercise, mean capillary filling pressure, systemic blood pressure, heart rate, evidence of medication tolerance, and incidence of medication side effects including headaches.

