#### *Pharmacologic Interventions*

At the conclusion of the first visit ISDN therapy will begin at a small dose (5 mg three times daily in those targeting 20-30 mg TID, less in patients < 40 kg) and be titrated up to goal three times daily over 2 weeks (see Table 2). The medication will be continued for 4 weeks once the target dose is reached. It is an organic nitrate commonly used to prevent angina and used frequently in heart failure as well. It acts upon vascular smooth muscles to cause vasodilation of the peripheral arteries and veins. It should be taken by mouth three times per day with water. It may be taken with or without food.

Patients not tolerating the medication will be instructed to call the clinic for adjustment of medications. Severe side effects to note include pre-syncope, syncope, and severe headache. The PI will assess the patient over the phone and ask them to come in if necessary. Conversation and any changes of

medications will be documented. Less severe symptoms such as mild lightheadedness or headache should attempt to be tolerated or treated with acetaminophen prior to calling the clinic.

Isosorbide dinitrate's clinically relevant interaction is with phosphodiesterase-5 inhibitors, a common medication in Fontan patients. There is a risk for excessive hypotension and therefore, will be a contraindication to enrollment in the trial. ISDN can also affect kidney function. For this reason, a basic metabolic panel will be taken at the start of the study and 1 week after initiation of ISDN.

Side effects will attempt to be reduced by a step-wise up-titration plan, use of acetaminophen for headache, and recommendation to return to previous dose if necessary which may enhance tolerability. Furthermore, patients will be followed up with by phone call 3-5 days after any change in medication.

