#### **Statistical Analyses**

Demographic and clinical characteristics of the patient population will be summarized using means and standard deviations or medians and interquartile ranges for continuous variables and frequencies and percents. for categorical variables.

The exercise endurance VO2 and all other study endpoints will be compared between the first and final visits.

Means and standard deviations will be calculated for exercise endurance at baseline and after one month of treatment. The 95% confidence intervals (CIs) for both the mean change and standard deviations will be calculated to obtain estimates of the population values under sampling variability. These values will provide us with a range of plausible values required to inform a rigorous sample size determination for a larger, confirmatory trial of isosorbide dinitrate on exercise capacity assuming no change under placebo. The mean change in VO2 divided the standard deviation will provide a measure of the standardized effect size. We expect a standardized mean difference of at least 0.2 standard deviation units in favor of the investigational agent would reflect a meaningful effect size to help support an encouraging (versus no effect) decision to proceed with a larger, confirmatory trial. We will also formally test whether the change in VO2 in response to isosorbide dinitrate is non-zero using a one-sample t-test or non-parametric alternative. This testing will be conducted using a one-sided alpha of 0.25 since our primary goal is to assess whether there may be preliminary evidence for efficacy and we are willing to accept greater risk of a type I error at this early stage of investigation.

Safety analyses will be conducted by reporting the counts of adverse events (AEs) and serious adverse events (SAEs). Lab values required to monitor patient safety will be determined by the investigators and DSMB. These values will be monitored and values reported to the DSMB over the course of the trial.

Estimates of preliminary efficacy and variability for secondary outcomes will be conducted using the approach described above for the primary outcome.

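### Nothing masks whoever measures liver stiffness, and the exams carry their date, so this secondary endpoint is open to an avoidable reading bias of unknown size

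*Combined protocol and SAP*

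**What the plan says.** The Study Design section states: "This will be a single arm, two-center prospective clinical trial of ISDN". There is no concurrent comparator. Under Pharmacologic Interventions, "At the conclusion of the first visit ISDN therapy will begin at a small dose". The description of Visit 6 places it before ISDN is discontinued, and Table 1 schedules the liver ultrasound at Visits 1 and 6 only.

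The Liver Ultrasound section says "Research imaging will include liver assessments of stiffness (ultrasound shear wave elastography", and that images are stored on a research archive "with exams and images labeled using subject study ID number and date of imaging/visit". The only review it describes has another purpose: "images will be reviewed by a study investigator or other radiologist for clinically important incidental findings". It also says "While a formal imaging report will not be rendered". It does not say who measures stiffness, whether this happens at the scanner or later, how the region is chosen, how many acquisitions count, or how they are summarised. No section of the document masks any assessor.

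The Abstract gives the expected direction: "The better hemodynamics associated with central vasodilation will result in greater exercise endurance and improved liver stiffness". Liver stiffness appears in the Secondary Objectives and among the secondary endpoints under Study Endpoints. The Statistical Analyses section says that "all other study endpoints will be compared between the first and final visits", and that efficacy and variability estimates for secondary outcomes follow the approach used for the primary.

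**The concern.** In this design, visit order and treatment status are the same thing. Subjects know they are on drug and there is no control group, so masking the measurement step is one of the few protections still available for stiffness. The plan does not use it, and the date on each exam shows the order to anyone who opens a subject's pair.

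The expected direction is written into the protocol, and the choices that could move a reading are not fixed. If a reader leaned, even unknowingly, towards lower values on the later scan, that lean would pass in full into the mean change. The estimate of the drug's effect on stiffness would then mix drug and reader, and the trial's data could not separate them.

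**Working it through.** **Does the label reveal treatment status?**
1. The drug starts at the end of Visit 1, after the baseline scan, so the first scan is off drug.
2. Visit 6 comes before the drug is stopped, so by plan the second scan is on drug.
3. Each exam carries study ID and date. With both exams of a subject open, the later date is the on-drug scan.
4. One date seen alone does not show status unless the reader also knows the enrolment date or has the other exam.

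**The plan's own figures.** The Sample Size Calculation gives precision for VO2 only, with n = 15 and SD 7.
- Half-width of the 95% interval for the mean: t(0.975, 14 df) × 7/√15 = 3.88; the plan says 3.9.
- 95% interval for the SD: 7 × √(14/χ²) gives 5.125 to 11.040, a width of 5.915; the plan says 5.9.

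Both reproduce. Neither concerns stiffness, for which the plan gives no mean, SD or reading variability.

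**How sensitive would the analysis be to a reading shift?** Inputs are n = 15 and the one-sided alpha of 0.25, which the plan states for VO2 and which is assumed here to carry over to stiffness. Let b be an assumed systematic shift towards lower stiffness, in SDs of the change, with no true drug effect.
- Observed change needed for a positive test: t(0.75, 14 df)/√15 = 0.692/3.873 = 0.179 SD.
- The test statistic follows a noncentral t distribution with 14 df and noncentrality b√15.

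| Assumed shift b | Chance of a positive test | Chance that the observed standardized change is at least 0.2 |
|---|---|---|
| 0 | 25.0% | 22.6% |
| 0.1 | 38.6% | 35.6% |
| 0.2 | 53.7% | 50.5% |
| 0.3 | 68.4% | 65.4% |
| 0.5 | 89.4% | 87.8% |

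The last column uses the 0.2 SD benchmark that the plan sets for VO2, applied to stiffness for illustration only. The table shows how little shift would matter; it does not estimate the shift. The 0.179 is the critical value of the test and would apply equally to any other source of before-after change.

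**The case against.** The labelling sentence is a storage and privacy rule, not a reading procedure, and the plan never says that one person reads the two scans together. A reader might infer that the stiffness reader knows which scan is on drug. The documents do not support that; they show only that a reader who sees both exams could tell. This limits the point to exposure, and exposure remains because nothing prevents it.

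Elastography returns a number, which may limit a reader's influence. That is fair, but the plan fixes neither the region nor which acquisitions count.

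Stiffness is one secondary endpoint in a 15-patient pilot. It is first in the Study Endpoints list, last in the Secondary Objectives list, and absent from the secondary endpoints in Study Design. The plan also says that null hypothesis testing is not directly tied to its aims, and its sentence extending the primary approach to secondary outcomes speaks of estimates, so the test may not carry over. All of this stands. It lowers the weight of the table, but a shifted estimate is biased whether or not it is tested.

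Recoding stored images does nothing if stiffness is measured at the scanner. This also stands, and the fix has to cover that case.

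A reader might extend the point to VO2 and venous pressure. The documents give weak support for that. Venous pressure is taken before exercise, every minute during it and for five minutes afterwards, and is converted to central pressure by a fixed equation. The exercise test ends when the subject can no longer continue, and relabelled files cannot mask that.

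**Conclusion.** The concern holds for liver stiffness: the plan leaves this endpoint open to a reading bias that could be reduced at little cost. The size is unknown and may be zero, because the documents contain no reading variability. The percentages rest on three assumptions: a systematic shift of the stated size, no drug effect, and the one-sided 0.25 level carried over to this endpoint.

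A reader might infer that biased stiffness readings would drive the decision on a confirmatory trial. The Statistical Analyses section does not support that: its encouraging-effect criterion is the standardized change in VO2. The primary endpoint and the justification of n = 15 are unaffected. What is at stake is the credibility of the stiffness estimate. Masking would remove one avoidable source of error, not the other before-after biases that come with having no control arm.

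**What to change.** 1. State who measures stiffness and when.
2. For endpoint measurement, make copies of the roughly 30 exams (15 subjects × 2) under a code that shows neither date nor visit. The coordinator keeps the key.
3. Have one existing study reader measure both exams of each subject in random order after that subject's Visit 6.
4. Fix in advance the rule for placing the region, the number of valid acquisitions, and the summary statistic.
5. If stiffness is measured during scanning, apply the same fixed rules there and keep the operator from seeing the baseline value.
6. Leave the date-labelled archive and the review for incidental findings as they are.

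The cost is some relabelling, later stiffness results and, if measurement was planned at the scanner, an added reading step. No patient procedure, extra reader or increase in sample size is needed. Masking stays partial, because the sonographer may know the visit.

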### **Quality of Life Survey**

All subjects will complete a quality of life PROMIS © survey at both the baseline visit and final visit. Based on age, the subject will complete their designated survey. If the subject age changes from baseline to final visit, the same survey will be completed for both time points.

### **Obtaining Informed Consent:**

Consent will be obtained before any study related procedures are performed. Our investigators and research coordinators will explain to eligible patients and their legal guardian the purpose of the study, the interventions, potential risks/benefits, and alternatives, and answer any questions. They will be informed that participation in the study is voluntary, that he/she may withdraw from the study at any time, and that this will in no way impact subsequent medical treatment or relationship with the physician. Those agreeing to participate will review and sign the IRB approved informed consent form. This form is written at a six grade level and arrangements can be made for illiterate families. The consent process will be documented in the informed consent progress note. A copy of the signed consent(s) will be kept in the patient's medical record and a copy will be provided to the patient.

Assent will be obtained in accordance with CCHMC policy for any participants 11-17.

### **Vulnerable Population**

Children and adolescents are required for this study because the Fontan surgery is typically performed in children between the ages of 3-6. These patients will be protected from coercion and undue influence by involvement of their parent/guardian in the informed consent process and attempt to attain assent from the child for all those enrolled in the study.

### **Investigational Agent:**

#### **Description**

Isosorbide dinitrate (ISDN) is an organic nitrate which dilates both arteries and veins and is indicated for the treatment of heart failure. Absorption of ISDN after oral dosing is nearly complete, but bioavailability is variable but averages 25%, with extensive first-pass metabolism. Serum levels reach their maximum within an hour.

